### SECTION V: RECRUITMENT/CONSENT AND ASSENT PROCEDURES

# 1. Recruitment Procedures:

a. Describe how potential participants will be identified and contacted, and by whom.

Fathers will be provided information about the study at the time of referral by DCF to the Parent & Family Development Program at Yale or the UCONN Health Center. Contact information for co-parents will be provided by DCF or other referral sourc at the time of the referral (which is current practice). Each father will be recruited and given initial screening by a study RA in person or over the phone. If a father expresses interest, an in-person or virtual Zoom appointment will be scheduled to complete informed consent and baseline measures.

Mothers of the fathers' youngest child will be contacted for initial screening and to assess her willingness to allow participation of herself and their shared child in the study. All research staff reaching out to female co-parents or current intimate partners will be trained on phone recruitment strategies used in previous studies by the PI and others to ensure safety of victims of IPV. These include: 1) asking whether she is free to talk now: 2) asking if it is ok to call back again; 3) asking if it is safe to leave messages on her voicemail or via text; and 4) during informed consent, making a plan for the safest way to contact her for follow-up data collection throughout treatment.

Mothers will be interviewed via zoom or in person on different days and encouraged to ensure their safety by choosing a location where they feel safe and away from the father to take the call. Fathers will not be informed of mothers' agreement to participate or the time or location of any contact the study team has with them. They will complete baseline interviews about their relationship history with the father, IPV in the relationship and the father's child maltreatment risk behaviors (hostility, yelling, spanking) toward the child. Mothers and intimate partner baseline interviews will take approximately 1-1 1/2to complete Mothers will be offered \$50 for completion of baseline interviews.

[name] will not be involved in the consent, recruitment, or enrollment of participants.

16

Are you collecting any information about the individuals prior to their signing a consent form? Yes  $\boxtimes$   $\;$  No  $\square$ 

If yes, indicate what information you will be collecting and how it will be gathered (phone screen, paper questionnaire, etc.)

An initial screen will be done with both Father and his co-parent. The RA will administer initial screen to father and co-parent either over the phone, in person or via Zoom. Fathers screen will include demographic matching information such as age, ethnicity, city of residence, income, employment history, substance abuse history etc. Co-parent screen will include IPV specific questions (e.g. severity of IPV and status of protective orders)

2. Indicate recruitment methods below. Attach copies of any recruitment materials that will be used.

□ Flyers	□ Internet/web postings	🗆 Radio
□ Posters	Mass email solicitation	🗆 Telephone
🗆 Letter	Departmental/Center website	□ Television
□ Through local NGO or other local contact	Departmental/Center research boards	🗆 Newspaper
□ Table set-up / in-person recruitment of public	$\Box$ Snowball sampling	
□ Classroom recruitment	□ Social Media (Twitter/Facebook):	
oxtimes Other: Referral by DCF case workers or IPV		
specialists		

# 3. Targeted Enrollment: Give the number of participants:

a. Targeted for enrollment at Yale for this protocol: Phase I: **180 Phase II: (180 fathers, 180 coparents and 180 children) = 540** 

b. If this is a multi-site study, give the total number of participants targeted across all sites (280 fathers, 280 coparents and 280 children) = 840

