# Phase I:

Seventy-five fathers of a biological child between 6 months and 11 years who are referred by the Department of Children and Families due to use of domestic violence in the last 12 months, the female co-parent of their youngest child and if different their current female intimate partners of more than 6 months, and their youngest biological child aged 6 months to11 years will participate for a total of up to 240 participants in this Phase 1B randomized controlled trial.

Female intimate partners who are not the co-parent of the youngest child will be contacted if they have been in a relationship with the father for at least 6 months at the time of consent.

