# Phase II:

The target sample is 280 father-coparent dyads and their 9 months to 11 year-old children recruited from CPS-involved families referred to the Parent and Family Development Program (PFDP) at Yale or the UCONN Health Center Outpatient Psychiatry Clinic. Participants will be randomized to either F4C (n = 140) or BIP (n = 140) following a baseline assessment. Half of F4C and BIP families will be treated at Yale and half at UConn Health. Yale will serve families in

Greater New Haven region, while UConn Health will serve families in the Greater Hartford region. The two sites are approximately a 45-minute drive apart.

5. **Describe** how access to the population will be gained in the study.

Fathers referred to the Parent and Family Development Program or UCONN Health Center by the CT Department of Children and Families (DCF) or the community due to IPV or child maltreatment risk will be provided information about the study and asked to complete an initial brief screening if they are interested in participation. He will be told that his screening questionnaire (which will include demographic matching information such as age, ethnicity, city of residence, income, employment history, SA history etc.) will be reviewed and he will be contacted to set up further assessment sessions if he is found eligible by the PI based on our study's requirements. This will provide the opportunity for contact with the mother to conduct phone screening with her related to IPV and her willingness for their shared child to participate. Female co-parent and intimate partner contact information will be provided on the referral from DCF or community referral source so that fathers are not providing this information, and this will limit the possibility of coercion.

6. **Participant classification:** Check off all classifications of participants that will be specifically recruited for enrollment in the research project. Will participants who may require additional safeguards or other considerations be enrolled in the study? If so, identify the population of participants requiring special safeguards and provide a justification for their involvement.

🛛 Healthy	□Fetal material, placenta, or dead fetus
Prisoners	□Economically disadvantaged persons
🗆 Employees	□Pregnant women and/or fetuses
□ Females of childbearing pote	ential
	
 
Healthy
 
Prisoners
 
Employees
 
Females of childbearing pote
 

Click or tap here to enter text.

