# 4. How was this estimate derived?

Phase I: Seventy-five fathers, the female co-parent of their youngest child, and their child will participate for a total of up to 225 participants. We intend to include all 75 fathers assigned to study interventions for intent to treat analysis. The planned sample size of 75 participants who will provide data for inclusion in our intention-to-treat analysis should provide sufficient power to detect clinically meaningful differences between and within treatment conditions as specified in our primary aims. A sample of 63 people provides power of 80% to detect a standardized treatment group differences at 18 weeks of d = 0.45. For purposes of power estimates, we assumed d = 0.45 will represent a potentially meaningful clinical difference in both our primary and mechanism outcomes. In a pilot study examining F4C on participant IPV effect size for outcome was d = 0.86. We will enroll 75 participants to accommodate a 16% loss to follow-up.

Using these procedures in prior studies, our rate of successful follow-up has ranged from 70-90%. With 280 participant families randomized and an aim of at least 70% completion, we expect to have 196 cases with complete treatment and follow-up data.

**4. Process of Consent/Assent** (*NOTE: When a study includes minors, parent provide permission [not consent] for the child's participation, and the child provides assent for participation)* 

Describe the setting and conditions under which consent/assent will be obtained, including parental permission or surrogate permission and the steps taken to ensure participants' independent decision-making.

Fathers will complete informed consent either in person or online via Yale's REDcap data system, in line with guidance on obtaining informed consent during the COVID-19 pandemic. Each will agree to have their female co-parent contacted for consent of participation of their shared child.

Mothers will complete informed consent related to their own participation and the participation of children in which they are the primary guardian. This will be completed online via Yale's REDcap system..

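### The Yale enrolment targets do not match the design: 180 fathers in Phase II where half of 280 is 140, and a Phase I target of 180 that equals neither 225 nor 240

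*Combined protocol and SAP*

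**What the plan says.** **Phase II.** Section V, Targeted Enrollment, gives the Yale target as "180 fathers, 180 coparents and 180 children) = 540" and the total across sites as "280 fathers, 280 coparents and 280 children) = 840". Section IV, Participant Population, Phase II, states "The target sample is 280 father-coparent dyads and their 9 months to 11 year-old children". It continues "Participants will be randomized to either F4C (n = 140) or BIP (n = 140) following a baseline assessment", and on the sites "Half of F4C and BIP families will be treated at Yale and half at UConn Health".

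The Analytic Plan (Phase II Hypotheses) carries other sizes. Aim 1 opens with 180 fathers per arm, then bases its power on 140 per arm and quotes 126 per arm after 30% attrition. Aim 2 relies on a total of 360, or 252 after attrition.

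**Phase I.** The Targeted Enrollment item reads "Targeted for enrollment at Yale for this protocol: Phase I: 180", with no unit, under a heading that asks for the number of participants. The next item, on how the estimate was derived, takes 75 fathers with their coparents and children, who "will participate for a total of up to 225 participants". Section IV, Participant Population, Phase I, also includes current partners who are not the coparent and arrives at 75 fathers "for a total of up to 240 participants".

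**The concern.** These are the enrolment sizes put to the IRB, for a study that the Data and Safety Monitoring Plan rates as above minimal risk and that enrols children and coparents exposed to violence. Each site should have one number of people, and it should follow from the design. At Yale it does not, in either phase.

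For Phase II the two lines of the Targeted Enrollment item cannot both hold alongside an equal site split. Recruitment and staffing at each site depend on which one is used. The mismatch also suggests that two Phase II sizes, 280 and 360 families, coexist in the current text. For Phase I the target differs from the figure in the item that is meant to explain it.

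**Working it through.** **Phase II inputs.** Total 280 families; 140 per arm; half at each site (Participant Population, Phase II). Yale target 180 fathers and 540 people; total 840 people (Targeted Enrollment).

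1. Reproduce the stated products: 180 × 3 = 540 and 280 × 3 = 840. Both are right, so the multiplication is sound and the input of 180 is what conflicts.
2. Yale's share under the stated split: 280 / 2 = 140 fathers; 140 × 3 = 420 people. Two sites: 2 × 420 = 840, which agrees with the stated total.
3. Difference: 180 − 140 = 40 fathers; 540 − 420 = 120 people.
4. Implied split: 180 / 280 = 64.3% at Yale; 280 − 180 = 100 families, or 35.7%, at UConn Health.
5. Possible source: 360 / 2 = 180. The attrition figures in the Analytic Plan fit the same size: 0.70 × 180 = 126 per arm and 0.70 × 360 = 252. With 140 per arm they would be 0.70 × 140 = 98 and 0.70 × 280 = 196. The 196 already stands in Section V, in the item on how the estimate was derived.

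**Phase I inputs.** 75 fathers, all referred to the Yale clinic (Research Plan, Phase I), so a second site cannot explain a lower Yale number. Stated target 180; stated totals up to 225 and up to 240.

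1. Father, coparent and child: 75 × 3 = 225, as stated in the derivation item.
2. The 240 is 15 higher (240 − 225 = 15). Its text also counts separate current partners, which would account for the difference, although the plan does not give the number 15.
3. The target of 180 is 225 − 180 = 45 below the first total and 240 − 180 = 60 below the second. Read as fathers, 180 would conflict with 75 more sharply still.

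**The case against.** The strongest reply is that this is clerical and that nothing statistical follows from it. Most of that stands.

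**Phase I power.** A reader might divide 180 by 3, get 60 families, and conclude that enrolment would stop short of the 63 fathers with complete data on whom the stated 80% power rests. The documents do not support this. The 180 is a target, not a stated ceiling, and it has no unit. Families need not be complete: a father may take part without his child (Inclusion Criteria; Evaluation of Capacity to Provide Consent/Assent). For illustration only, 75 fathers + 75 coparents + 30 children = 180, which includes every father. The plan states 75 fathers consistently and puts all 75 in the intention-to-treat analysis. Since 225 and 240 are both upper limits, the gaps of 45 and 60 compare a target with maxima.

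**Phase II power.** A reader might also take the 64:36 split as a loss of power. Site is not among the stratification variables as listed, and the Aim 1 analysis does not mention it. At a fixed total of 280 with 140 per arm, an unequal site split leaves the stated power calculation unchanged. The UConn figure of 100 is itself obtained by subtraction; the plan states no UConn target.

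**Which figure is wrong.** If 360 families were intended, 180 at Yale would be the correct half and the 280 and 840 would be wrong. This cannot be excluded, but 280 is the better supported size. It appears in the Research Plan, Participant Population and both Section V items, and it matches the 140 per arm in the Phase II aims.

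None of this removes the contradiction. No text describes 180 as a screening allowance, a reserve or planned over-enrolment.

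**Conclusion.** The Yale targets are wrong as written. On the 280-family design with equal sites, the Phase II figure is 40 fathers and 120 people too high. The Phase I figure agrees with neither total that the plan gives. Both results are plain counts and need no assumption beyond the plan's own statements of 280 families, an equal site split, three people per family and 75 Phase I fathers.

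That the Phase II 180 was carried over from a 360-family design is an inference. It rests on 180 being half of 360 and on 126 and 252 being 70% of 180 and 360. The consequence is limited to enrolment and site targets. No loss of Phase I power is shown, and the site split does not change Phase II power while the total stays at 280.

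**What to change.** First confirm the Phase II size.

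- **If 280:** in Targeted Enrollment set Yale to 140 fathers, 140 coparents and 140 children = 420, with the same for UConn Health and 840 in total. In the Analytic Plan change 180 per arm to 140 and 360 to 280, and at the stated 30% attrition change 126 to 98 and 252 to 196. Then check that the Aim 1 and Aim 2 power statements still hold at those retained numbers. Leave the equal-split sentence alone unless a different split is really intended.
- **If 360:** keep 180 and 540 at Yale, and change 280 to 360, 840 to 360 × 3 = 1,080, 140 per arm to 180 and 196 to 252 wherever they occur.

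For Phase I, change only the figure in Targeted Enrollment: to 225, or to 240 if separate current partners are counted, with a note of which definition applies. The 225 and 240 elsewhere can stand once each is labelled.

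With 280 confirmed, the cost is a few figures in one amendment and no change of design. Choosing 360 would mean 80 more families than the enrolment item now totals.

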# 4. How was this estimate derived?

Phase I: Seventy-five fathers, the female co-parent of their youngest child, and their child will participate for a total of up to 225 participants. We intend to include all 75 fathers assigned to study interventions for intent to treat analysis. The planned sample size of 75 participants who will provide data for inclusion in our intention-to-treat analysis should provide sufficient power to detect clinically meaningful differences between and within treatment conditions as specified in our primary aims. A sample of 63 people provides power of 80% to detect a standardized treatment group differences at 18 weeks of d = 0.45. For purposes of power estimates, we assumed d = 0.45 will represent a potentially meaningful clinical difference in both our primary and mechanism outcomes. In a pilot study examining F4C on participant IPV effect size for outcome was d = 0.86. We will enroll 75 participants to accommodate a 16% loss to follow-up.

Using these procedures in prior studies, our rate of successful follow-up has ranged from 70-90%. With 280 participant families randomized and an aim of at least 70% completion, we expect to have 196 cases with complete treatment and follow-up data.

**4. Process of Consent/Assent** (*NOTE: When a study includes minors, parent provide permission [not consent] for the child's participation, and the child provides assent for participation)* 

Describe the setting and conditions under which consent/assent will be obtained, including parental permission or surrogate permission and the steps taken to ensure participants' independent decision-making.

Fathers will complete informed consent either in person or online via Yale's REDcap data system, in line with guidance on obtaining informed consent during the COVID-19 pandemic. Each will agree to have their female co-parent contacted for consent of participation of their shared child.

Mothers will complete informed consent related to their own participation and the participation of children in which they are the primary guardian. This will be completed online via Yale's REDcap system..

Children in the study will be up to age 12 so will not sign informed consent but an assent will be used. For children under the age of 7 a verbal assent only will collected. The study procedures will be explained to them and their verbal assent to participate in play with their dads will take place prior to beginning the play assessment. Children 7 and older will complete a signed assent.

5. Evaluation of Participant(s) Capacity to Provide Informed Consent/Assent: Indicate how the personnel obtaining consent will assess the potential participant's ability and capacity to consent to the research being proposed, if applicable.

All potential participants (mothers, and fathers) will receive an explanation of the study, risks, benefits, and procedures with a trained research assistant in an individual, secure online Zoom meeting or in person. Research assistants who are attaining consents will be trained by the Pls. This will include observing [name] conducting practice informed consent procedures and then conducting the procedures in role play with them for practice. Participants will be asked to sign the compound consent form in person or via Yale REDcap, if they wish to participate following resolution of any questions and clear indication that the participants understand the nature of the study and the consent. We routinely use an informed consent quiz to assure all prospective participants understand all aspects of the protocol and its requirements. Fathers will have study interventions explained and options for participation explained. Fathers' treatment at the PDFP, or other treatments offered by the CT Department of Children and Families will in no way be influenced by their participation in the study. If they opt not to participate or decide to withdraw, they will continue to receive care as usual. The certificate of confidentiality will ensure that information collected as part of the research evaluation cannot be subpoenaed. This detail will be explained to participants and be part of the informed consent quiz to ensure understanding by participants.

Children will be recruited into this study to participate in brief self-reports of their symptoms (for those 7 and older) and father-child observational assessments. This will provide an observational measure of father-child interactions providing an additional measure of change related to parenting and child maltreatment risk. Fathers will be able to participate without their children to reduce any risks to the children for retaliation for their lack of participation. Study research assistants will describe the study procedures to the child and ask if they would like to participate. Verbal agreement to participate and behavioral compliance without undue pressure from the father will be taken as assent from children under 7. For those over 7 a written assent will be collected. If a play session cannot begin or must be ended, father and child will be compensated for the attempt to provide data to minimize risk to the child for being uncooperative. If a play session

or child report assessment does not proceed, the father will continue in the study to randomization and treatment assignment.

6. Documentation of Consent/Assent: Specify the documents or verbal scripts that will be used during the consent/assent process. Copies of all documents should be appended to the protocol, in the same format that they will be given or spoken to participants.

A script to introduce the play assessment to children is included with the protocol. RAs will use this script with children prior to beginning the sessions.

7. Non-English Speaking Participants: Explain provisions in place to ensure comprehension for research involving non-English speaking participants. Translated copies of all consent materials must be submitted for approval prior to use. Do you speak the local language? Will you require a translator? (If so, please elaborate on how the translators will be trained).

N/A this study will include English speaking only participants.

**8.** Are any of the study procedures likely to yield information subject to mandatory reporting requirements? (e.g. HIV testing – reporting of communicable diseases; parent interview -incidents of child abuse, elderly abuse, etc.). Please verify to whom such instances will need to be reported.

It is possible that procedures will result in information subject to mandatory reporting of child abuse or harm to self or others. Participants will clearly be informed of the limits of this confidentiality, which are in cases of suspected child abuse or neglect, and imminent risk for harm to self or others (particularly intimate partner or child).

Confidentiality regulations and limits to these regulations will be adhered to as follows: The MPIs, along with co-investigators [name], [name] and have extensive experience in directing and running clinical programs. All five investigators are licensed clinical psychologists who are mandated reporters and are required to report child abuse as required by law. They are also required to break confidentiality regulations in the event a participant is suicidal or homicidal.

